6. STUDY TREATMENT

6.1 Description of Study Drug and Supplies

DUPILUMAB (dupilumab) Injection is supplied as a sterile, preservative-free, clear to slightly opalescent, colorless to pale yellow solution for subcutaneous injection. DUPILUMAB is provided as a single-dose pre-filled syringe with or without needle shield in a 2.25 mL siliconized Type-1 clear glass syringe. The needle cap is not made with natural rubber latex. Each pre-filled syringe delivers 300 mg dupilumab in 2 mL which also contains L-arginine hydrochloride (10.5 mg), L- histidine (6.2 mg), polysorbate 80 (4 mg), sodium acetate (2 mg), sucrose (100 mg), and water for injection, pH 5.9.

Under no circumstances is the Investigator allowed to release these clinical supplies for use by another physician not named on Form FDA 1572 or to administer study drug to a patient who is not enrolled in this study. Study drug must be dispensed at an institution specified on Form FDA 1572.

6.2 Drug Preparation

6.2.1 General Guidelines and Precautions

Men will be treated with dupilumab 600 mg s.q. on day 1, and then 300 mg s.q. on days 8,15, 22, 29, 36, 43.

Injection or allergic reactions may occur with the administration of monoclonal antibodies and other protein-based therapeutics. Precautions for anaphylaxis should be observed during DUPILUMAB administration. Supportive measures may include, but are not limited to: epinephrine, antihistamines, corticosteroids, IV fluids, vasopressors, oxygen, bronchodilators, diphenhydramine, and acetaminophen. Please refer to **Section 6.4.3** for specific guidelines regarding the management of drug reactions. Supportive care measures consistent with optimal patient care will be provided throughout the study according to institutional standards.

6.2.2 DUPILUMAB

- Inspect drug products visually for particulate matter and discoloration prior to administration. Discard vial if solution is cloudy, there is pronounced discoloration (solution may have pale-yellow color), or there is foreign particulate matter.
- The desired amount of DUPILUMAB should be withdrawn from the vial(s) and diluted to the appropriate final concentration with 0.9% Sodium Chloride Injection USP, according to the instructions provided.Discard partially used vials of DUPILUMAB
- Administration of study drug should begin immediately after preparation but no later than 6 hours after preparation. If there is a delay in administration of study drug such that it will not be administered on the day of preparation, the Principal Investigator should be notified immediately. Instructions on how to proceed will be provided.

6.2.3 Placebo or Control

There will be neither placebo nor active control drug for this study.

6.3 Study Drug Administration

Do not mix DUPILUMAB with, or administer as an injection with, other medicinal products.

6.4 **Potential Adverse Events and Supportive Care Measures**

6.4.1 Grading of Administration Reactions

Injection reactions will be categorized as follows:

• Grade 1: mild reaction; intervention not indicated; (see Section 6.4.3);

- Grade 2: moderate reaction: responds promptly to symptomatic treatment [e.g., antihistamines, non-steroidal anti-inflammatory drugs (NSAIDS), narcotics, IV fluids]; prophylactic medications indicated for ≤ 24 hours;
- Grade 3: prolonged reaction: recurrence of symptoms following initial improvement; hospitalization indicated for clinical sequelae (e.g., renal impairment, pulmonary infiltrates);
- Grade 4: life-threatening consequences; pressor or ventilatory support indicated;
- Grade 5: death.

The above grading scale is the CTCAE v 4.03 grading scale for CRS, which is nearly identical to the CTCAE v 4.03 grading scale for injection reaction and allergic reaction, and therefore considered appropriate for grading all injection reactions in this study, irrespective of the underlying mechanism of the reaction. The Sponsor's Medical Monitor or designee should be contacted immediately if questions arise concerning the grade of the reaction.

6.4.2 Premedications and Prophylaxis

For DUPILUMAB, the following suggested guidelines (which may be modified by the investigator according to the institutional guidelines for management of anaphylaxis reactions) are measures to be followed if a drug reaction is noted after s.c. administration to avoid potential reactions with future administration.

Treatment (guidelines to be followed):

- Acetaminophen 650 mg
- Diphenhydramine 50 mg or appropriate dose of equivalent H1 antagonist
- Ranitidine 300 mg or appropriate dose of equivalent H2 antagonist at the discretion of the investigator
- Hydrocortisone 20 to 40 mg (dose selected at the discretion of the Investigator)

Prior to next administration (guidelines to be followed):

- Acetaminophen 650 mg
- Diphenhydramine 50 mg or appropriate dose of equivalent H1 antagonist
- Ranitidine 300 mg or appropriate dose of equivalent H2 antagonist at the discretion of the investigator
- Hydrocortisone 20 to 40 mg (dose selected at the discretion of the Investigator)

6.4.3 Dose Management for Adverse Events considered related to DUPILUMAB

Temporary interruptions of DUPILUMAB may be required in the event of treatment-related toxicity. General guidelines for specific toxicity regarding dosing and treatment are provided below. All toxicities will be graded according to NCI CTCAE v4.03 (see **Section 7.1.2**).

6.4.3.1 Grade 1 or 2 AEs

Study drug administration may continue despite observation of drugrelated low grade adverse events (CTCAE grade 1 or 2). If the investigator in his/her medical judgment considers that a low grade AE is of clinical significance or inordinately prolonged, the Investigator may, at his/her discretion, delay treatment to allow for resolution. Necessity to delay for more than two consecutive doses will require the patient to permanently discontinue study drug. No dose reductions are allowed.

6.4.3.2 Grade 3 or 4 AEs

Drug administration should be held upon observation of AEs of \geq Grade 3 severity to enable patient management, monitoring of the resolution of the event, and assessment of the relatedness of the event. An AE of \geq Grade 3 that is considered related to DUPILUMAB will result in discontinuation of therapy unless other specified in the protocol. For AEs associated with liver function test abnormalities, drug administration may resume upon resolution of the AE to \leq Grade 1 severity unless more than seven days elapse before return to \leq Grade 2 severity or fourteen days have elapsed from the last dose. In this case, the AE is considered dose limiting, two consecutive doses will have been missed, and study drug administration should be discontinued. Following a single missed dose, the treatment schedule should resume as if no delay had occurred and the patient receive all intended DUPILUMAB doses.

6.5 Concomitant Therapy

DUPILUMAB is the only cancer drug to be administered routinely in this study. No concomitant anti-cancer therapy will be given.

All concomitant medications and blood products administered during the patient's participation in the study until the post treatment follow-up visit must be recorded in the source document and on the electronic Case Report Form (eCRF). All changes in infusions, including interruptions and their duration as well as reductions in rate and duration must be recorded.

The following rules concerning concurrent treatment(s) will apply in this study:

Any other anti-neoplastic therapies including but not limited to chemotherapy or other small molecules, biologics, or radiotherapy are not allowed.

- Patients may not receive other investigational drugs during the period of study participation.
- Because DUPILUMAB has a mechanism of action dependent upon inhibiting macrophages, the use of corticosteroids should be limited to the extent possible. Chronic doses of corticosteroids in excess of 10 mg daily of prednisone or equivalent is prohibited other than for the management of drug-related adverse experiences. Steroids may be employed in the treatment of suspected DUPILUMAB-associated immune-inflammatory or autoimmune AEs in consultation with the Sponsor.
- The use of other immuno-suppressive agents is prohibited, unless they are being used to treat an adverse event.
- Use of granulocyte colony stimulating factor, granulocyte-macrophage colony stimulating factor or other growth factors is prohibited.

Patients may receive the following concurrent therapy:

- Antiemetics, antidiarrheals, anticholinergics, antispasmodics, antipyretics, antihistamines, analgesics, antibiotics and other antimicrobials, histamine receptor antagonists or proton pump inhibitors, and other medications intended to treat symptoms or signs of disease.
- Transfusions such as red blood cells and platelets are permitted to treat symptoms or signs of anemia or thrombocytopenia and should be documented on the concomitant medication form.

6.6 Restrictions

6.6.1 Prior Therapy

Prior therapy restrictions are described in the inclusion/exclusion criteria specified in Section 3.

6.6.2 Fluid and Food Intake

There are no requirements for fasting and no restrictions for fluid and food intake by the patients during the study.

6.6.3 Patient Activity Restrictions

There are no restrictions on patient activities and no requirement for patient confinement during the study.

6.7 Treatment Compliance

DUPILUMAB will be administered by healthcare professionals under the supervision of the Investigators. Records of DUPILUMAB dose calculation, administration, and dosing regimen will be accurately maintained by site staff. The monitor will review dose calculation, administration and regimen as well as medication accountability during investigational site visits and at the completion of the study.

6.8 Packaging and Labeling

DUPILUMAB will be supplied in bulk, open-label, single-use vials. All investigational product will be labelled with a minimum of the protocol number, directions for use,

storage conditions, expiry date (if applicable), batch number, the statements "For clinical trial use only," and/or "CAUTION: New Drug – Limited by Federal (United States) Law to Investigational Use," and the Sponsor's name and address. Please see the Pharmacy Manual for detailed information about the packaging of the study drug.

6.9 Storage and Accountability

The vials containing study drug should be stored at $2^{\circ}-8^{\circ}$ C ($36^{\circ}-46^{\circ}$ F) and must not be frozen or shaken. Protect from sunlight. To ensure compliance with storage conditions, temperature logs will be maintained.

Because there is no preservative and drug loss occurs over time, administration of study drug should begin immediately after preparation but no later than 6 hours after preparation (see Pharmacy Manual). If there is a delay in administration of study drug such that it will not be administered on the day of preparation, the Clinical Project Manager should be notified immediately. Instructions on how to proceed will be provided.

The Investigator or his/her designee is required to maintain accurate drug accountability records. A binder containing instructions and the required accountability documentation will be provided to the Investigator or his designee. When the study is completed, copies of study drug accountability records must be sent to the Sponsor. The original drug accountability records must be maintained with the rest of the documentation in accordance with Section 9.3 of the protocol.

Additional details regarding storage, handling, and accountability can be found in the Pharmacy Manual.

6.10 Investigational Product Disposition at End of Study

Upon completion or termination of the study, all unopened vials of study medication must be returned to MacroGenics or its representative, unless the site has received written authorization from MacroGenics to destroy study drug at the site. All drug returns to MacroGenics or its representative must be accompanied by the appropriate documentation and be clearly identified by protocol number and study site number on the outermost shipping container. If MacroGenics approves the destruction of drug at the site, the Investigator must ensure arrangements are made for proper disposal and that appropriate records of disposal are documented and maintained and copies provided to the Sponsor.

7. ADVERSE EVENTS AND REPORTING REQUIREMENTS

An adverse event (AE) is defined as any untoward medical occurrence (symptom, sign, illness or experience) that develops or worsens in a research patient during a clinical study or within 30 days post-treatment, regardless of causality. This includes adverse clinical or laboratory findings, any adverse drug reaction (ADR), an illness with onset during the study, or an exacerbation of a preexisting illness or condition. Cancer progression should not be considered an AE, unless the investigator believes that the study treatment exacerbated the patient's condition. Exceptions are if disease progression results in death or hospitalization while a patient is on study, in which case the disease progression is considered a serious AE. Abnormal findings on physical examination or diagnostic procedures are also considered AEs if: they are associated with clinical signs or symptoms; they require therapeutic intervention or additional

diagnostic testing; they lead to dose modifications/termination of the study drug; or they are considered clinically significant by the investigator. All observed or reported AEs, regardless of their suspected causal relationship to the study drug, should be recorded on the Case Report Form (CRF).

The NCI CTCAE version 4.0 will be used for adverse event descriptions and grading (http://ctep.cancer.gov/protocolDevelopment/electronic applications/docs/ctcaev3.pdf). These criteria are summarized in Appendix B. The type and severity of an AE, as well as its potential link to the study drug(s), will determine whether the event requires expedited reporting in addition to routine reporting. For all AEs, the investigator must pursue and obtain information to adequately determine the causality and outcome of the event, and to assess whether it meets criteria for a serious AE. In addition, follow-up of AEs should continue until the event and any sequelae resolve or stabilize at a level acceptable to the investigator and/or the medical monitor.

7.1 **Recording and Grading**

7.1.1 Recording

All observed or volunteered adverse events, regardless of treatment group, severity, suspected causality, expectedness, or seriousness will be documented on the CRF.

A clinically significant change in a physical examination finding or an abnormal test result (*i.e.*, laboratory value) should be recorded as an AE, if it:

- is associated with accompanying symptoms •
- requires additional diagnostic testing or medical or surgical intervention •
- leads to a change in study dosing or discontinuation from the study •
- requires additional concomitant drug treatment or other therapy, or
- is considered clinically significant by the investigator

An abnormal test result that is subsequently determined to be an error does not require recording as an AE even if it originally met one or more of the above criteria.

7.1.2 Grading severity

All adverse events will be graded for intensity on a scale of 0 to 5, according to the NCI CTCAE version 4.0 (see Table 2 and Appendix B). These criteria can be found at

http://ctep.cancer.gov/protocolDevelopment/electronic applications/docs/ctcaev3 .pdf

Table 2 Intensity of Adverse Event

Grade	Description
0 (none)	No adverse event or within normal limits.
1 (mild)	Transient or mild discomfort; generally non-progressive; no limitation in daily activities; no medical intervention required.

2 (moderate)	Mild/moderate limitation in daily activities; some assistance may be required; no/minimal medical intervention required.
3 (severe)	Marked limitation in daily activities; some assistance usually required; medical intervention is required.
4 (life- threatening)	Extreme limitation in daily activities; major assistance required; significant medical intervention required.
5 (death)	Fatal adverse event.

7.1.3 Attributing causality

After grading for severity, the investigator must evaluate all clinical AEs and abnormal laboratory values for possible causal relationship to the study drug(s). Causality attribution will be decided using the criteria outlined in Table 3.

Relationship	Description
Unrelated	AE is clearly not related to the study drug (An event that does not meet any of the criteria below).
Unlikely	AE is doubtfully related to the study drug (An event that follows a reasonable temporal sequence after drug administration; that follows a known or expected response pattern; but that could more reasonably be explained by other characteristics of the patient's clinical state).
Possible	AE may be related to the study drug (An event that follows a reasonable temporal sequence after drug administration; that follows a known or expected response pattern; but that could just as readily be attributed to a number of other factors).
Probable	AE is likely related to the study drug (An event that follows a reasonable temporal sequence after drug administration; that follows a known or expected response pattern; that is confirmed by stopping/reducing the drug dose; and that could not be reasonably explained by the characteristics of the patient's clinical state).
Definite	AE is clearly related to the study drug (An event that follows a reasonable temporal sequence after drug administration; that follows a known or expected response pattern; and that is confirmed by improvement on stopping/reducing the drug dose and reappearance on repeated exposure).

Table 3 Relationship of Adverse Event to Study Drug

Abnormal laboratory values of clinical significance that were present at baseline and did not change in severity or frequency during experimental therapy and those that can obviously be attributed to underlying disease will be recorded as unrelated and will not be considered when evaluating study drug toxicity.

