7.3 Serious Adverse Events and Serious Adverse Drug Reactions

The investigator must assess each event to determine if it meets the criteria for classification as a serious adverse event (SAE) or serious adverse drug reaction (ADR). An SAE/ADR is defined in the Code of Federal Regulations (21CFR312.32) as any event that:

- results in death
- is life-threatening
- results in inpatient hospitalization or prolongation of existing hospitalization
- results in persistent or significant disability or incapacity
- results in congenital anomaly or birth defect
- is medically significant in the opinion of the investigator

All SAEs that occur any time while a patient is on study (*i.e.*, as soon as the informed consent has been signed) or within 30 days of the last dose of study drug administration must be documented, regardless of the suspected relationship to the investigational agent(s). Any SAE occurring more than 30 days after the last dose of the study drug(s) must be recorded if a causal relationship to the investigational agent(s) is suspected.

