7.5.2 Reporting requirements for the Sidney Kimmel Comprehensive Cancer Center (SKCCC)

The principal investigator will notify the appropriate regulatory agencies of any SAEs occurring during the study period, regardless of causality. These agencies include the Sidney Kimmel Comprehensive Cancer Center (SKCCC) Data and Safety Monitoring Committee (DSMC), and the Institutional Review Board (IRB) and the Institutional Biosafety Committee (IBC) of the Johns Hopkins Medical Institutions (JHMI). For SAEs that are fatal, life-threatening, or treatment-related but non-life threatening: IRB/IBC reporting by the PI is required within 3 days. For unrelated SAEs, IRB/IBC reporting by the PI is required within 15 days. All other AEs should be documented on CRFs and submitted according to the standard data management guidelines.

Adverse event information will be collected continuously throughout the duration of the study. Participants will be instructed to notify their treating provider of any new signs or symptoms, and providers will actively assess patients for adverse events at each visit (including by evaluation of laboratory studies). The investigator will assess each AE for its severity and for its relationship to the study drug, and all events Grade 1 or higher will be documented on CRFs and then reported as described above within the required time frame. Any AE occurring while a patient is on study (*i.e.* after informed consent has been signed) or within 30 days of study termination requires reporting. AEs occurring later than

this must still be reported if a causal relationship with the study drug is suspected.

For all AEs, the investigator must pursue and obtain information to adequately determine the causality and outcome of the event, and to assess whether it meets criteria for a SAE. In addition, follow-up of an AE is required until the event either resolves or stabilizes. Initial reporting of an AE should include at a minimum the patient number, age, the dose at which the event occurred, and the type and severity of the event. Follow-up information including causality, duration, outcome, action taken, and concomitant medications should be reported soon thereafter.

The principal investigator must keep copies of all CRFs and other AE information, including correspondence with the IRB for as long as required to comply with national and international regulations (generally at least 3 years after study completion).

7.5.3 Research Involving).

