10.4 Safety Analysis

10.4.1 Evaluation of adverse events

Treatment-emergent adverse events will be translated from investigator terms to MedDRA version 6.0 terminology and summarized (number and percentage of patients) for all patients who receive at least one dose of the study drug(s). Adverse event summaries will be organized by body system, frequency of occurrence, intensity (*i.e.*, severity grade), and causality or attribution. Patients who experience an adverse event more than once will be counted only once. The occurrence with the maximum severity will be used to calculate intensity.

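### Table 3 cannot score a new type of adverse event above Unrelated, and it ranks some unexplained known-type events below the same event with a rival cause

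*Combined protocol and SAP*

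**What the plan says.** Section 7.1.3 directs the investigator to decide causality with Table 3, which has five categories.

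- **Unrelated** is the residual: "AE is clearly not related to the study drug (An event that does not meet any of the criteria below".
- **Unlikely** needs plausible timing, a known or expected pattern, and another explanation that is more reasonable.
- **Possible** needs plausible timing and an event "that follows a known or expected response pattern; but that could just as readily be attributed to a number of other factors".
- **Probable** needs plausible timing, the known pattern, and an event "that is confirmed by stopping/reducing the drug dose; and that could not be reasonably explained by the characteristics of the patient's clinical state".
- **Definite** needs plausible timing, the known pattern, improvement on stopping or reducing the drug, and recurrence on re-exposure.

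Three provisions use the result:

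- Section 6.4.3.2: a Grade 3 or higher event "considered related to DUPILUMAB will result in discontinuation of therapy", unless the protocol specifies otherwise.
- Section 7.5.2: SAEs that are fatal, life-threatening or treatment-related go to the IRB/IBC within 3 days. The rest wait longer: "For unrelated SAEs, IRB/IBC reporting by the PI is required within 15 days".
- Section 10.4.1: AE summaries are organised by, among other things, "intensity (*i.e.*, severity grade), and causality or attribution".

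Section 7.2 defines unexpected events but gives no rule for attributing them.

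**The concern.** An attribution scale should rise with the evidence for a causal link. This one has two gaps.

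First, familiarity of the event is a condition of causality, so a toxicity not seen before has no category above Unrelated, however strong the other evidence. Safety and tolerability is a secondary objective (1.2). The clinical trials summarised in 2.2.3 are in atopic dermatitis, so new or peri-operative toxicity is what this trial could add.

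Second, a known-type event with no rival explanation needs positive dechallenge to reach any category, because Unlikely and Possible are worded around a rival explanation. Removing the rival explanation can therefore lower the score.

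At stake are a misleading attribution column, a relatedness trigger that does not fire as its authors presumably intended, and slower IRB/IBC notice for some serious events.

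**Working it through.** The plan gives no figure to reproduce here; the check is on the logic of Table 3.

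**1. Enumerate the definitions.** Inputs, all from Table 3: plausible timing (yes/no), known pattern (yes/no), other explanation (more likely / equally likely / none), and dechallenge state (not positive / positive / positive with positive rechallenge).

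Profiles: 2 × 2 × 3 × 3 = 36.

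**2. No known pattern.** This covers 36 / 2 = 18 profiles. Read as whole definitions, all 18 score Unrelated. One of them has plausible timing, no other cause, positive dechallenge and positive rechallenge.

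**3. Plausible timing and known pattern.** This leaves 3 × 3 = 9 profiles:

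| Other explanation | Dechallenge not positive | Dechallenge positive | Rechallenge also positive |
|---|---|---|---|
| More likely | Unlikely | Unlikely | Unlikely and Definite |
| Equally likely | Possible | Possible | Possible and Definite |
| None | **Unrelated** | Probable | Probable and Definite |

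Exactly 1 of the 9 falls to Unrelated. In the first column the score goes Unlikely, Possible, Unrelated as the rival explanation weakens, so the order reverses.

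**4. The other reading.** If the criteria in the Unrelated definition are single elements, a well-timed event meets one of them and is not Unrelated. It still satisfies none of the other four definitions, so it has no category.

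**5. When dechallenge is unavailable.** The reduction limb is closed for low-grade events: "No dose reductions are allowed" (6.4.3.1). The last dose is on day 43, surgery on day 57, and safety assessment runs to post-operative day 60 (5.1, 10.1).

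- End of window: 57 + 60 = day 117.
- Days after the last dose: 117 − 43 = 74.
- Of these, before surgery: 57 − 43 = 14. After surgery: 117 − 57 = 60.

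After day 43 no planned dose remains to stop. Washout is also slow: 2.2.1 gives median times to non-detectable drug of 10 weeks (two-weekly dosing) and 13 weeks (weekly dosing) after the last steady-state dose. Applied here as a rough guide, that is day 43 + 70 = 113 to day 43 + 91 = 134. The same section puts steady state at week 16, so these times are only indicative for a course ending on day 43.

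In the 60 post-operative days surgery is often a rival cause, and a known-type event would then score Unlikely or Possible. The second gap therefore applies mainly to the 14 pre-operative days and to later events that surgery does not plausibly explain.

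**6. Trace the uses.**

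| Provision | Depends on attribution? |
|---|---|
| Causality summaries (10.4.1) | Yes |
| Discontinuation after a related Grade ≥3 AE (6.4.3.2) | Yes |
| IRB/IBC clock, SAE not fatal or life-threatening (7.5.2) | Yes: 3 or 15 days, a 12-day difference |
| Grade ≥3 toxicity boundary (10.1) | No attribution condition written |
| Recording AEs on the CRF (7.1.1) | No |
| Documenting on-study SAEs (7.3) | No |

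**The case against.** The strongest defence is that Table 3 guides judgement. Unrelated is headed as clearly not related, and an investigator facing a well-timed, unexplained event would not choose it. The pattern phrase is undefined and could include effects expected from the mechanism. For peri-operative events 7.4 adds joint judgement by the principal investigator and urologists.

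This shows the outcome is not forced, but it does not close the gap. On the single-element reading the event has no category, and nothing in the table says that mechanism counts as expected. Delayed wound healing shows the problem: 7.4 lists it, and 2.3.1 says M2 macrophages promote wound repair. Two investigators could disagree on whether it meets the pattern requirement, and so on whether it can leave Unrelated.

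The defence is right about reach. A reader might infer more than the documents support:

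- **That the stopping rule is biased.** The boundary in 10.1 counts Grade ≥3 AEs with no relatedness condition. The last paragraph of 7.1.3 does exclude some items from toxicity evaluation, but only certain laboratory abnormalities: those unchanged from baseline or obviously due to the disease.
- **That new toxicities go unseen.** All AEs are recorded whatever their causality or expectedness (7.1.1), and unexpected reactions go to the principal investigator within 24 hours (7.5.1). Drug is held for any Grade ≥3 AE while relatedness is assessed (6.4.3.2).
- **That late SAEs are lost.** An SAE more than 30 days after the last dose "must be recorded if a causal relationship to the investigational agent(s) is suspected", but 7.3 also requires all on-study SAEs to be documented regardless of relationship. Section 7.5.2 covers any AE on study or within 30 days of study termination. The late test is also suspicion of causality, not a Table 3 category.
- **That most events are misattributed.** With timing fixed as plausible, 9 + 1 = 10 of 18 profiles score Unrelated, but these are unweighted logical cells under one reading, not event rates. Likewise 74 / 117 = 63% of the window follows the last dose, but 60 of those 74 days follow surgery.

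**Conclusion.** The point holds as a defect in a mandatory rule, with limited consequences. A new type of event cannot be placed above Unrelated under either reading of Table 3. A known-type event with no rival cause and no positive or assessable dechallenge is ranked below the same event with a rival cause. No other section I found corrects this.

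The damage is confined to the causality summaries, the relatedness trigger for discontinuation, and a possible move from 3 to 15 days for IRB/IBC reporting of SAEs that are neither fatal nor life-threatening. The primary endpoint and the toxicity boundary are untouched. The number of affected events cannot be estimated from the documents.

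The conclusion rests on two assumptions: that Table 3 is applied as written, and that an Unrelated score counts as not related in 6.4.3.2 and 7.5.2. The protocol never states which categories count as related.

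**What to change.** Amend Table 3 and its companions:

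- Make the known or expected pattern supportive evidence in the four upper categories, not a requirement.
- Define Unrelated positively: no plausible timing, or another cause clearly established.
- Allow Probable when there is no reasonable alternative explanation and dechallenge is either positive or not assessable, for example because dosing is complete.
- Assess expectedness separately under 7.2.
- Check that the Appendix C SAE form uses the same categories. Its labels are clipped in the text available here, so a mismatch is not certain.

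The cost is a wording amendment, somewhat more events scored Possible or Probable, and slightly more 3-day reports. No change to dosing or to any clinical rule is proposed.
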